3.7 Center pooling strategy

The data will come from one center. The statistical analyses will not be performed by center.

3.8 Coding dictionaries

Adverse events and medical history will be coded using the latest available version of the Medical Dictionary for Regulatory Activities (MedDRA[®]) Medications will be coded according to the latest version of the World Health Organization Drug Dictionary (WHODD) (Version SEP/2017). Medical procedures will not be coded.

3.9 Changes to protocol-defined analyses

- Changes in the analysis of PK variables (section 1.1 of the protocol):
 - The analysis of CL/F_{ss} (apparent total clearance at steady-state) will be conducted only for PSL and not for the two metabolites of PSL (as planned in protocol section 1.1).
 - The variable $MR_{C_{max,ss}}$ (Metabolic ratio for $C_{max,ss}$) will be analysed for PSL and two metabolites of PSL instead of the variable $MR_{C_{max}}$ (Metabolic ratio for C_{max}).
- Change in the name of an analysis datasets (section 9.1 of the protocol).
 - The “Enrolled Set” will be renamed as the “All Study Participants” analysis set in the SAP and will include all study participants who sign the informed consent form.

4 STATISTICAL/ANALYTICAL ISSUES

4.1 Adjustments for covariates

Not applicable.

4.2 Handling of dropouts or missing data

In general, there will be no imputation of missing data unless otherwise stated below.

Missing data will be handled as described in the sections below for safety laboratory and PK results. No other imputations will be performed.

4.2.1 Pharmacokinetics

The 95% CI lower and 95% CI upper should be left blank if the standard deviation (or equivalently, the geometric CV) is 0. Measurements of PK concentrations that are below the limit of quantification (BLQ) and which are occurring prior to t_{max} will be imputed with half of the lower limit of quantification (LLOQ/2), except for embedded BLQ values (between two measurable data points) which will be treated as missing, for the purpose of calculating the geometric mean and its 95% CI, the geometric CV, the arithmetic mean and standard deviation for summaries and figures. Post- t_{max} , BLQ values will be treated as missing. Descriptive statistics of concentrations will be calculated if at least 2/3rd of the individual data points are quantifiable (\geq LLOQ).

For all individual PK concentration figures any concentrations that are BLQ will be regarded as missing, with the exception of pre-dose BLQ measurements which will be imputed with zero (to capture lag-time) for linear scale plots.

The following rules will apply for PK data listings:

- Values below the LLOQ will be reported as “(BLQ)” in the listings

The following rules will apply for PK summaries:

- Descriptive statistics of plasma concentrations will be calculated if more than 2/3rd of individual data points are quantifiable (\geq LLOQ) at the given time-point. However, if $n < 3$, then only n , minimum and maximum will be presented, and the median will also be presented if $n = 3$. The other descriptive statistics will be left blank.
- For t_{max} , $t_{1/2}$, and $t_{1/2ss}$ only N , median, minimum and maximum will be displayed into the summary statistics,
- For plasma concentration summaries, all BLQ values will be replaced by “LLOQ/2 and missing values will be excluded.
- When the mean value includes one or more replaced BLQ values then a footnote will be included to say “contains one or more BLQ value replaced by half the LLOQ value”.
- For the individual figures, any concentrations that are BLQ will be regarded as missing, with the exception of pre-dose BLQ measurements which will be imputed with zero for linear scale plots.
- If no participants have data, only $n = 0$ will be presented. The other descriptive statistics will be left blank.
- The geometric CV will be calculated using the following formula where SD_{log} is the standard deviation from the log-transformed data:

$$\text{Geometric CV (\%)} = \sqrt{[\exp(SD_{log}^2) - 1]} \times 100$$

- The PK analysis will be performed in accordance to the Guideline on performing NCA analysis dated 08 Nov 2017, and BLQ values will be treated as stated in this document for the NCA analysis.

4.2.2 Safety laboratory data

The rules for handling values that are BLQ or above the limit of quantification (ALQ) in the safety laboratory data will be the same as those described for PK data in [Section 4.2.1](#).

4.2.3 Electrocardiogram data

For the 12-lead ECG data, all calculations of changes from Baseline and descriptive statistics will be based on the mean of the triplicate assessments at each time point. In the event that there are not 3 available measurements at a given time point, the mean will be calculated based on the number of measurements for which data are provided.

4.2.4 Dates and times

Partial dates may be imputed for the following reasons:

- Classification of AEs as treatment-emergent
- Classification of medications as prior or concomitant

Imputed dates will not be shown in the listings; all dates will be displayed as reported in the database.

The following rules will be applied for partial start dates:

- If only the month and year are specified and the month and year of the first dose of study medication is not the same as the month and year of the start date then use the 1st of the month, or the date of screening if this is later (if the latter imputation results in an end date that is earlier than the start date, then use the 1st of the month). If time is missing this will be imputed as 00:00h
- If only the month and year are specified and the month and year of the first dose of study medication is the same as the month and year of the start date, then the date of the first dose of study medication will be used. If this results in an imputed start date that is after the specified end date, then use the 1st of the month, or the date of screening if this is later (if the latter imputation results in an end date that is earlier than the start date, then use the 1st of the month). If the imputed date is the date of dosing then time will be imputed as the start time of the dosing (i.e., event will be regarded as treatment-emergent)
- If only the year is specified, and the year of the first dose of study medication is not the same as the year of the start date then January 01 will be used. If time is missing this will be imputed as 00:00h
- If only the year is specified, and the year of the first dose of study medication is the same as the year of the start date, then the date of the first dose of study medication will be used. If this results in an imputed start date that is after the specified end date, then January 01, or the date of screening if this is later will be used (if the latter imputation results in an end date that is earlier than the start date, then January 01 will be used). If the imputed date is the date of first dose of study medication then time will be imputed as the start time of the study medication intake (i.e., event will be regarded as treatment-emergent)

The following rules will be applied to partial stop dates:

- If only the month and year are specified, then use the last day of the month
- If only the year is specified, then use December 31 of the known year
- If the stop date is completely unknown, do not impute the stop date

Missing or partially missing dates and/or times will be imputed as described in [Table 3-1](#):

[Calculation rules for duration of adverse events](#) [Table 3-1](#) for the calculation of duration of each AE. Adverse event duration is computed in and reported in day and time format: xx d hh:mm.

Table 3-1: Calculation rules for duration of adverse events			
Data availability	Onset date/time	Outcome date/time	Calculation rules
Complete data	D1/T1	D2/T2	Duration = [(D2 – D1)*24 + (T2 – T1)]/24 d
End time missing	D1/T1	D2/--	End time is substituted by time 23:59h (=23.98 in decimal format) Duration = <[(D2 – D1)*24 + (23.98 – T1)]/24 d
Start time missing	D1/--	D2/T2	Onset time is substituted by time 00:00h Duration = <[(D2 – D1)*24 + T2]/24 d
Start and end time missing	D1/--	D2/--	Duration = <D2 – D1 + 1
Start day and time missing	--/--	D2/T2	Duration = [(D2 – D0)*24 + (T2 – T0)]/24 d For a participant in the FAS, D0 and T0 are the date and time of first administration of study medication and for screen failures, D0 is the date of the screening visit and T0 = 00:00h
End day and time missing	D1/T1	--/--	If the stop date is missing, duration will not be calculated.
Start and end date missing	--/--	--/--	If the stop date is missing, duration will not be calculated.

FAS=full analysis set; PSL=padsevonil.

4.3 Handling of repeated and unscheduled measurements

All repeated and unscheduled measurements will be presented in the data listings, where applicable. The following general rules will apply to all repeated and unscheduled measurements:

- For repeated measurements obtained prior to the first dose of study medication the latest value (which may be scheduled or unscheduled) will be used in the calculation of the descriptive statistics
- For repeated measurements obtained at the designated Baseline visit, the latest value (which may be scheduled or unscheduled) will be defined as the Baseline provided that this occurred prior to the first dose of study medication
- Unscheduled and repeated measurements will not be used in the descriptive statistics at time points after first dose of study medication
- Unscheduled measurements performed for the End-of-Study/End-of-Treatment (EOT) visit will be assigned to the EOS/EOT Visit (Section 4.4) and analyzed accordingly as an EOS/EOT Visit.

4.4 Handling of measurements obtained at the early withdrawal visit

Study participants who withdraw early from the study for any reason, including those withdrawn from study medication, will be asked to return for the EOS Visit as soon as possible after the last dose of study medication.

4.5 Interim analyses and data monitoring

Not applicable.

4.6 Multicenter studies

This study is planned to be conducted at one site. Thus, there is no plan to explore sites effect in the analysis.

4.7 Multiple comparisons/multiplicity

Not applicable.

4.8 Use of an efficacy subset of participants

Not applicable.

4.9 Active-control studies intended to show equivalence

Not applicable.

4.10 Examination of subgroups

If PK effects by age group or gender are observed (i.e., between adult and elderly study participants) and if there are at least 5 participants within each subgroup category within the elderly age groups or gender groups based on the related subgroup analysis, then subgroup analyses may be performed.

An ANOVA with age group as the fixed effect and the primary PK parameters as the dependent variable will be performed. If the age group fixed effect is significant for at least one primary PK parameter at $\alpha = 0.1$ significance level, then a subgroup analysis based on age group (≥ 65 to 74 years old and ≥ 75 years old) will be performed within the elderly cohort.

Similarly, an ANOVA with age group and gender as the fixed effects and the primary PK parameters as the dependent variable will be performed. If the gender fixed effect is significant for at least one primary PK parameter at $\alpha = 0.1$ significance level, then a subgroup analysis based on gender (male and female) will be performed within both the adult and elderly cohorts.

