9.3 Planned safety and other analyses

9.3.1 Pharmacokinetic analyses

Pharmacokinetics will be determined by non-compartmental analysis with Pharsight Phoenix[®] WinNonlin[®] v6.3 (or higher) software using the PK-PPS.

Pharmacokinetic parameters of PSL and its 2 major metabolites [REDACTED] will be computed using the actual blood sampling time points.

The plasma concentration-time profiles, urine amounts, and PK parameters of PSL and its 2 major metabolites [REDACTED] will be summarized by age group (adult [18-64 years] and elderly study participants [≥ 65 years]) and treatment period using descriptive statistics. If PK effects by age group are observed (ie, between adult and elderly study participants), subgroup analyses may be performed within the elderly age group (age [≥ 65 to 74 years old and ≥ 75 years old] and gender).

Individual plasma PSL and its major metabolites concentration-time profiles will be displayed graphically on a linear-linear scale and semi-logarithmic scale (including spaghetti plots). Geometric mean plasma concentrations-time curves including 95% confidence intervals (CIs) will be displayed by cohort.

For the SD and MD periods of the study, primary PK parameters (AUC and C_{max}) will be assessed in adults and elderly study participants with analysis of variance (ANOVA). Point

estimates for the ratio of geometric means between adults and elderly study participants (and per category, if deemed necessary), and the respective 2-sided 90% CIs, will be computed using the least squares means and the root mean squares of error from the ANOVA of the log-transformed data with subsequent exponential transformation. Interparticipant variability on PK parameters will be derived from these analyses.

The relationship between PK parameters of PSL (and metabolites) and creatinine clearance, age (numerical), hepatic laboratory parameters (eg, bilirubin, ALT, and AST) will be evaluated using a graphical approach or correlation and linear regression techniques.

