2.3 Study design and conduct

This is a Phase 1, open-label study to evaluate the effect of age on the PK, safety, and tolerability of oral PSL in 2 cohorts of at least 10 adult (18 to 64 years, inclusive) study participants (Cohort A) and 18 elderly (≥ 65 years) study participants (Cohort B).

The study utilizes a single dose (SD) and a multiple dose (MD) design. Period 1A is the SD Period and consists of a single dose of PSL followed by a Washout Period. Period 1B is the MD Period and consists of PSL up-titration, maintenance, and tapering during the Treatment Period, followed by a Washout Period. Both adult and elderly study participants will take part in the SD and MD Periods.

The total study duration for each study participant is up to 28 days for Screening plus 22 days from Day 1 through the EOS/EOT Visit (up to 50 days in total).

The study consists of Screening, a Baseline Visit, Treatment Period, and Follow-up Period (End-of-Study/End-of-Treatment [EOS/EOT] Visit).

Screening will be conducted at the study site(s) 3 to 28 days prior to check-in to the study site. Eligible study participants in the 2 age cohorts will be matched per gender for body weight if feasible, i.e., the elderly study participants will be recruited first, and per gender, matched for body weight with adult study participants. Individual cases will be discussed with the Sponsor as needed. In each age cohort, there will be a homogenous repartition between male and female study participants, with at least 3 participants in each gender. To allow for an investigation of potential age-dependent effects, the elderly study participant cohort will also preferably include the following categories: at least 3 males and 3 females from ≥ 65 to 74 years old, and at least 3 males and 3 females ≥ 75 years old.

Study participants will check into the study site on Day -1 for the Baseline Visit and will undergo assessments as specified in the Schedule of Activities (Table 2-1).

The Treatment Period consists of Period 1A (PSL SD administration) on Days 1 to 7 and Period 1B (PSL MD administration) on Days 8 to 21.

In Period 1A, study participants will receive a single oral dose of 200mg PSL on Day 1, at approximately 8:00am, 30 minutes after a light meal. No study drug will be administered on Days 2 to 7; assessments will be conducted during this time as specified in the Schedule of Activities (Table 2-1). Days 2 to 7 are designated as a 6-day washout.

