3.6 Treatment assignment

Tables will be presented by age group (Adults (18-64 years) or Elderly (≥ 65 years)) and overall. Listings will be presented by age group and study period as described in Section 3.2.2. PK summaries will be presented for PSL and two metabolites of PSL during the treatment periods (SD and MD)

Table 3–2: Padsevonil administration

Cohort A (adults; n=at least 10) and Cohort B (elderly; n=at least 18)																		
Treatment Period																	Follow-up Period	
Period 1A (SD)							Period 1B (MD)										EOS/EOT Visit	
Day	1	2	3	4	5 to 7	8	9	10	11	12	13 morning	13 evening	14	15	16	17 to 21	22	
	Washout															Washout		
PSL Dose (mg)	200					50 BID	100 BID	200 BID	200 BID	200 BID	200	100	100 BID	100 BID	50 BID			
	Plasma	Plasma	Plasma	Plasma							Plasma							
	Urine	Urine	Urine	Urine							Urine							

BID=twice daily; EOS=End-of-Study; EOT=End-of-Treatment; MD=multiple dose; PK=pharmacokinetic(s); PSL=padsevonil; SD=single dose

Note: BID dosing will be at approximately 8:00am and 8:00pm.

Note: To allow age-dependent effects, elderly study participants will include preferably the following categories: at least 3 males and 3 females from ≥65 to 74 years old and at least 3 males and 3 females ≥75 years old. The elderly study participants will be analyzed as one group. If an effect of age category is observed on PK or safety parameters, the effect of the age category will be explored.

This document cannot be used to support any marketing authorization application and any extensions or variations thereof.

REDACTED COPY

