9 PHARMACOKINETICS

The calculation of the PK parameters of PSL and two of its metabolites () will be performed by the Pharmacokinetic Pharmacodynamic Modeling and Simulation Department, ICON PLC. All PK TELs will be produced by ICON PLC SAS programming (Early Phase).

Pharmacokinetic concentrations and PK parameters will be summarized using the PK-PPS and listed on the FAS by study participants. Figures of summaries will be based on the PK-PPS and figures of individual concentrations will be based on the FAS.

Pharmacokinetic parameters of PSL and two metabolites of PSL () will be computed using the actual sampling time points.

The plasma concentration-time profiles, urine amounts, and PK parameters of PSL and two metabolites of PSL () will be summarized by age group (adult [18-64 years] and elderly study participants [≥ 65 years]) and treatment period using descriptive statistics.

If PK effects by age group or gender as described in Section 4.10 observed, then the analysis of the primary PK variables will be repeated for subgroups within the adult and elderly cohorts.

Individual plasma PSL concentration-time profiles along with the individual plasma concentration-time profiles of the two metabolites of PSL will be displayed graphically on a linear-linear scale and semi-logarithmic scale (including spaghetti plots). Geometric mean plasma concentrations-time curves including 95% confidence intervals (CIs) will be displayed by cohort.

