For the single dose (Period 1A) and multiple dose (Period 1B)) periods of the study, primary PK parameters (Single dose C_{max} , AUC_{0-t} , AUC and multiple dose: $C_{max,ss}$, AUC_{τ}) will be assessed in adults and elderly study participants with analysis of variance (ANOVA). Point estimates for the ratio of geometric means between adults and elderly study participants (and per category, if deemed necessary), and the respective 2-sided 90% CIs, will be computed using the least squares means and the root mean squares of error from the ANOVA of the log-transformed data with subsequent exponential transformation. Inter-participant variability on PK parameters will be derived from these analyses.

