9.3 Analysis of other pharmacokinetic variables

The other PK parameters and their analysis are the following:

- The relationship between PK parameters (AUC_t, AUC, AUC_{0-t}, CL/F, CL_R and t_{1/2}) of PSL and two metabolites of PSL and creatinine clearance, age (numerical), hepatic laboratory parameters (e.g., bilirubin, ALT, and AST) will be evaluated. The relationship will be displayed graphically using scatterplots, and the correlation between the PK parameter and the hepatic function test or age will be evaluated using linear regression, considering the PK parameter as the dependent variable and the hepatic function test or age as the independent variable.
- The point estimate and the 95% CI for the median differences for t_{max} between the adult and elderly cohorts will be computed according to the Hodges-Lehmann method.

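### The comparison of ages 65–74 and 75-and-over depends on the pooled adult-versus-elderly test, so a rise in exposure confined to the oldest participants may get no category ratio

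*SAP*

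**What the plan says.** SAP 2.3 explains why two elderly categories are recruited: "To allow for an investigation of potential age-dependent effects, the elderly study participant cohort will also preferably include the following categories", preferably with at least 3 men and 3 women in each, so at least 6 aged 65–74 and 6 aged 75 or over.

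SAP 4.10 then sets the condition for analysing them. An ANOVA is fitted with adult versus elderly as the fixed effect. "If the age group fixed effect is significant for at least one primary PK parameter" at 0.1, the 65–74 versus 75-and-over analysis "will be performed within the elderly cohort". At least 5 participants per category are also required. SAP 9 carries this forward: if effects as described in 4.10 are seen, "then the analysis of the primary PK variables will be repeated for subgroups within the adult and elderly cohorts".

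Four other places bear on the point:

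- SAP 3.6, note to Table 3-2, pools the elderly by default and adds: "If an effect of age category is observed on PK or safety parameters, the effect of the age category will be explored". That trigger is an effect of age category, which is not the trigger in 4.10.
- SAP 9.1 mentions geometric mean ratios "and per category, if deemed necessary", without a criterion.
- Protocol 9.3.1 says that, if an adult-versus-elderly effect is observed, "subgroup analyses may be performed within the elderly age group".
- SAP 9.3 plans scatterplots and a linear regression with no condition attached, "considering the PK parameter as the dependent variable and the hepatic function test or age as the independent variable". Its parameter list includes the AUCs but not Cmax or Cmax,ss.

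**The concern.** The trigger tests a different contrast from the one it controls. Pooling averages participants aged 75 and over with those aged 65–74. If exposure rises mainly in the oldest, the pooled difference shrinks towards zero, and the spread between the two categories also enters the residual error. The test is therefore weakest in the situation where the category split is most informative.

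The study exists to evaluate the effect of age. If exposure rises mainly at 75 and over, the pooled ratio understates it for that stratum, and the plan may then supply no prespecified ratio there. Under SAP 1, analyses added after database lock are supplementary ones to be explained in the study report. Even when the trigger is met, SAP 4.10 places the analysis inside the elderly cohort, so a 75-and-over versus adult ratio is not clearly specified.

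**Working it through.** **Inputs from the documents.** CV 40%, 10 adults and 18 elderly (SAP 2.4, Protocol 9.8). Five primary parameters: Cmax, AUC0-t and AUC after the single dose; Cmax,ss and AUCτ after multiple doses (SAP 2.2.1.1). Trigger at 0.1 on any one of them (SAP 4.10); for a two-level factor the F test is a two-sided t-test.

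**Assumptions not in the documents.** 9 or 6 of the 18 elderly aged 75 or over (6 is the preferred minimum). Correlation between the five log parameters 0.9 to 0.6. The effect patterns below. For the age regression, ages uniform on 18–64, 65–74 and 75–85, and a two-sided 0.1 level, because SAP 9.3 states none.

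**1. The plan's own figure.** Log SD σ = √ln(1 + 0.4²) = 0.3853. With 9 per group, the noncentrality is ln 2 / (0.3853 × √(2/9)) = 0.693 / 0.1816 = 3.82. The one-sided 0.05 t-test with 16 df has 97.7% power (96.9% if 0.40 is taken as the log SD). The stated 97% is reproduced. With 10 versus 18 and all elderly at 2-fold, the trigger is met on a single parameter in 99.7% of trials.

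**2. Dilution.** With a 2-fold effect only at 75 and over, the pooled ratio is 2^(9/18) = 1.41 or 2^(6/18) = 1.26.

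**3. One parameter.** The pooled test is then significant in 56% (9 of 18) or 30% (6 of 18) of simulated trials. Over CVs of 30% to 60% this runs from 73% to 38%, or from 38% to 22%. The direct 75-and-over versus adult contrast in a three-category model (25 df) has standard error 0.3853 × √(1/10 + 1/9) = 0.177 or 0.3853 × √(1/10 + 1/6) = 0.199, hence noncentrality 3.92 or 3.48 and power 98% or 96% at two-sided 0.1.

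**4. Any of five parameters**, 100,000 simulated trials per setting. Ranges run from correlation 0.9 to 0.6.

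| Ratio at 65–74, then at 75+ | Trigger met, 9 of 18 aged 75+ | Trigger met, 6 of 18 aged 75+ |
|---|---|---|
| 1, 2 | 71–85% | 44–59% |
| 1, 1.5 | 45–61% | 30–44% |
| 1.25, 1.5 | 77–89% | 71–85% |
| 1.25, 2 | 93–98% | 84–94% |
| 1.41, 2 | 98–100% | 95–99% |
| 1, 1 (no effect) | 19–31% | 19–31% |

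The trigger fails while the direct contrast on a given parameter is significant in 14–28% (9 of 18) or 37–53% (6 of 18) of trials for the 2-fold step, and in 2–6% or 5–13% for 1.25-fold then 2-fold.

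**5. The age regression as a fallback.** For the 2-fold step, a regression on at least one of the three AUCs is significant in 86–93% or 65–76% of trials. Trigger or regression: 88–95% or 67–80%.

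**6. Price of removing the condition.** With no age effect, at least one category-versus-adult contrast is nominally significant at 0.1 in 32–49% of trials, against 18–29% with the condition in place. The 90% CI factor is exp(t × σ × √(1/10 + 1/n)), with t the 95th percentile. With 25 df it is 1.35, 1.40 and 1.43 for n = 9, 6 and 5. The pooled factor (n = 18, 26 df) is 1.30.

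**The case against.** The strongest reply is that the large losses need a sharp step: 2-fold at 75 and over and nothing at 65–74. No section predicts that. Protocol 4.3 describes hepatic and renal function declining with age, which suggests a graded effect, and there the trigger is usually met. The 6-of-18 figures use the preferred minimum, not a planned split. A lower correlation between parameters also helps: at 0.4 the step effect meets the trigger in 91% or 68% of trials. All of this stands and limits how serious the point is.

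Pooling with conditional exploration is also a deliberate choice, present in the protocol, and the 0.1 level on any of five parameters is lenient. That justifies pooling as the main analysis. It does not justify leaving out a supportive estimate in the categories the study recruits for. SAP 10.4.1 already summarises markedly abnormal vital signs for 18–64, 65–74 and 75-and-over without any condition.

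SAP 9.1 does name category ratios with 90% CIs, so the method is arguably prespecified, and read with SAP 9 it may imply a comparison with adults. The decision to produce them, however, is left to judgement. The ungated regression and the individual plots make it less likely that a late rise goes unseen, and Protocol 9.3.1 does not confine the age analysis to AUCs. But a slope is not an exposure ratio for the oldest participants.

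Lastly, more category contrasts mean more chance findings, and a disclaimer will not stop every reader from noting intervals that exclude 1. This is a real cost and is counted below.

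**Conclusion.** The concern holds. The plan commits to the age-category analysis of primary PK only through a test that dilutes a late effect, and nothing elsewhere guarantees a category ratio. For a 2-fold effect confined to 75 and over, the trigger fails in about 15–29% of trials with 9 of 18 aged 75 or over, and in about 41–56% with 6 of 18 (100% minus the values in the table). For graded effects reaching 2-fold it fails in at most 16%.

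These figures rest on the plan's CV of 40% and on the assumed age split, correlations and effect patterns. The pooled primary result is unaffected. The change is worth making because it is cheap and serves the study's stated purpose; it does not repair an invalid analysis.

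**What to change.** Amend the SAP before database lock, as SAP 1 requires. In 4.10, remove the 0.1 condition for age category only and leave the gender rule as it is. Suggested text:

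> Each log-transformed primary PK parameter will also be analysed in an ANOVA with a three-level age category (18–64, 65–74, 75 years and over). For each elderly category, the geometric mean ratio to adults and its two-sided 90% CI will be given as a supportive estimate, provided every category has at least 5 participants. No claim of significance will be based on these ratios.

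Keep the pooled elderly-versus-adult comparison as the primary result. Bring the note to Table 3-2 in SAP 3.6 and the cross-reference in SAP 9 into line, and record the departure from Protocol 9.3.1 in SAP 3.9.

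The cost is one paragraph, one table and one residual degree of freedom; no new data are needed. The category intervals are wider (times or divided by about 1.35–1.43, against 1.30 pooled) and there is no multiplicity control. With no age effect, nominally significant category contrasts rise from 18–29% to 32–49% of trials, so the ratios must be labelled as estimates.
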